5.2.3.2. Change from Baseline in 6MWT over 26 Weeks

The actual values, changes from baseline, and percent changes from baseline in 6MWT total distance walked in 6 minutes [REDACTED] will be presented descriptively for each time point by treatment group. Results will also be graphically displayed by means of subject profile plots, boxplots over time by treatment group for the actual values, and line plots of the mean (+/- SE) over time by treatment group for (percent) changes from baseline.

The change from baseline in 6MWT over 26 weeks will be compared between treatment groups by means of an ANCOVA model at Week 26 (as defined in Section 3.3.3) including treatment and stratum as categorical covariates and baseline 6MWT distance as continuous covariates. LS

means and 95% CIs will be presented per treatment group as well as the LS mean difference between treatment groups with 95% CI.

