6.4.5. Functional Exercise Capacity Testing: 6-Minute Walk Test

A 6MWT will be performed at the study center to assess pulmonary function. The 6MWT will be performed based on the ATS recommendations [27] and at baseline visit (Visit 2) and Visit 9 / EOT [REDACTED]

[REDACTED] Contraindications for performing the 6MWT are provided in [Appendix 3](#).

[REDACTED]

[REDACTED]

[REDACTED]

[REDACTED]

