Appendix 3 Contraindications for 6-Minute Walk Test

Absolute contraindications:

- Unstable angina during the previous month [27]
- Myocardial infarction during the previous month [27]
- Oxygen saturation measured by pulse oximetry <88 % after 10 minutes of rest of breathing room air or at baseline oxygen flow rate [30].

Relative contraindications [27]

- Resting heart rate >120 beats per minute
- SBP >180 mmHg
- DBP >100 mmHg

Source: [27]

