2.2.2. Secondary Endpoints

- Safety and tolerability changes over time (baseline to 26 weeks).
- Time to any of major events (whichever occurs first) defined as:
 - Death (all-cause and respiratory-related)
 - First hospitalization (all-cause and respiratory-related)
- Change from baseline 26 weeks in functional exercise capacity, assessed by the 6MWT at Week 26.
- Change from baseline until 26 weeks in quality of life measures, assessed by the St. George's Respiratory Questionnaire (SGRQ) total score and domains and proportion of SGRQ responders.
- Plasma concentrations of GLPG1205, nintedanib and pirfenidone.

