3.4.1.2. Handling of Missing Result Data

No imputation will be done of missing result data. That is, an observed cases (OC) analysis will be performed. Details on the sensitivity analyses to investigate the impact of missing data on efficacy parameters are described in Section 6.2.

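### The only visible 6MWT test is an observed-case ANCOVA at Week 26, so subjects who die or become unable to walk leave the comparison, with no supplementary analysis to show the effect

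*SAP*

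**What the plan says.** The endpoint is change in "functional exercise capacity, assessed by the 6MWT at Week 26" (SAP 2.2.2). Per the schedules of activities, the walk is done at screening, Visit 2, Visit 9 and, for early stoppers, the EOT visit. No other on-treatment walk is planned.

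Protocol 6.4.5, which schedules the Visit 2 and Visit 9/EOT tests, states: "Contraindications for performing the 6MWT are provided in" Appendix 3. The visible text does not confine them to screening. Appendix 3 lists three absolute contraindications: "Oxygen saturation measured by pulse oximetry <88 % after 10 minutes of rest" (on room air or the baseline oxygen flow), "Myocardial infarction during the previous month", and unstable angina over the same period. Its heart-rate and blood-pressure limits are only relative.

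SAP 5.2.3.2 gives descriptive summaries and one inferential comparison, made "by means of an ANCOVA model at Week 26 (as defined in Section 3.3.3", adjusting for treatment, stratum and baseline distance. SAP 3.4.1.2 states: "No imputation will be done of missing result data. That is, an observed cases (OC) analysis will be performed". It points to Section 6.2 for sensitivity analyses on missing efficacy data, but Section 6 of the SAP is the reference list. The sensitivity analyses that do exist (SAP 5.2.2.2) concern the primary FVC endpoint.

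**The concern.** Inclusion criterion 9.1 requires every subject to walk at least 150 m at screening with no Appendix 3 contraindication. A contraindication at Week 26 is therefore new since screening. In IPF, new resting hypoxia may be the progression that the drug is meant to prevent, so the distance would be missing because of the outcome.

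An observed-case ANCOVA is sound if, within arm, missingness depends only on stratum and baseline distance. It is not sound when missingness depends on the subject's condition at Week 26. The 6MWT is more exposed than the other continuous endpoints. FVC has six scheduled on-treatment visits plus slope and repeated-measures analyses, and SGRQ has a Week 12 value. The 6MWT has one time point and one test.

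The result will be used: the SAP added this ANCOVA to the protocol's descriptive plan (SAP 5.5), tests it at two-sided 5% (SAP 5.2.1), and includes the 6MWT in the interim package meant for planning later studies (SAP 4.2).

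**Working it through.** **1. The plan's own figure.** Protocol 7.1 concerns FVC, the only endpoint with sample-size figures. Mean difference = 0.5×50 + 0.5×80 = 65 mL. With 10% dropout, 40/20 becomes 36/18, so SE = 200×√(1/36 + 1/18) = 57.74 mL. P(>40 mL) = 1 − Φ((40 − 65)/57.74) = 66.7%, and P(>20 mL) = 1 − Φ((20 − 65)/57.74) = 78.2%. The stated 67% and 78% are reproduced and not disputed. What carries over here is the arm sizes and the 10% dropout. No 6MWT figure is given.

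**2. Who has a Week 26 value.** SAP Table 2 sets Week 26 as Days 163–197.

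- Death before the test: no value.
- Absolute contraindication or physical inability at Visit 9: no value.
- Early stopper whose EOT walk is before Day 163: the walk falls in an earlier window. It appears in summaries but not in the Week 26 ANCOVA.
- Visit 9 moved because of COVID-19: Day 183 − 28 = 155 to Day 183 + 56 = 239, so some walks fall outside the window. This loss is administrative. SAP 3.3.3 promises reassignment of late visits for efficacy results, while 5.2.2.2.4 details it for the primary endpoint only.

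The first two groups are lost because of their condition, and the visible text gives them no value or rank.

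**3. Illustrative size.** Every input here is an assumption. Let change in distance be normal with SD 1, mean 0 on placebo and mean D on GLPG1205. Subjects below a common level c cannot be tested. If a share p of placebo is untestable, c = Φ⁻¹(p), and the untestable active share is Φ(c − D). The expected observed mean in an arm with mean μ is μ + φ(c − μ)/(1 − Φ(c − μ)).

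Example with D = 0.30 and p = 10%: c = −1.28. Placebo observed mean = 0.1755/0.90 = 0.195. Active observed mean = 0.30 + 0.1142/0.943 = 0.421. Observed difference = 0.226 SD, which is 75% of 0.30.

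| Placebo untestable (of 20) | D = 0.30: active untestable, observed difference, kept | D = 0.50: active untestable, observed difference, kept |
|---|---|---|
| 5% (1) | 2.6%, 0.25, 84% | 1.6%, 0.43, 86% |
| 10% (2) | 5.7%, 0.23, 75% | 3.7%, 0.39, 78% |
| 15% (3) | 9.1%, 0.21, 68% | 6.2%, 0.36, 71% |
| 20% (4) | 12.7%, 0.19, 63% | 9.0%, 0.33, 66% |

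Reversing the arms gives the same shrinkage of a harm.

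**The case against.** **Size.** No document figure shows that many subjects would become untestable in 26 weeks. Entry requires FVC ≥50% predicted, DLCO ≥30% predicted and a 150 m walk, and saturation may be measured on baseline oxygen flow. The 15% and 20% rows exceed the plan's allowance for all dropout; at 5%, 84–86% of the effect is kept. This stands, and the table is illustration only.

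**Erasure.** A reader might infer that the analysis could erase a benefit. That needs the drug to do nothing for those who can still walk and to act only by preventing untestability. Nothing in the documents supports that. When the effect acts on everyone, the table shows shrinkage.

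**Direction.** Nor do equal untestable shares guarantee no bias. Suppose 10% of each arm is untestable at −100 m, and walkers change by 0 m on active and −20 m on placebo. The full difference is (0.9×0 − 10) − (0.9×(−20) − 10) = 18 m, against 20 m observed, a slight overstatement. So understatement is usual, not certain.

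**Reach of the bar.** A reader might also infer that Appendix 3 bars every ill subject, or that early EOT walks are discarded. It has three absolute bars, two of them cardiac; other losses come through the observed-case rule. Early EOT walks do appear in the descriptive summaries.

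**Other outputs.** Adjudicated death and hospitalization are analysed separately (SAP 5.2.3.1), and disposition and numbers per window are tabulated by arm (SAP 5.1.3). Differential loss would therefore be partly visible. These outputs do not correct the walk estimate, and they miss a living, non-hospitalized subject too hypoxic to walk.

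**Redaction.** Protocol 6.4.5 and SAP 5.2.3.2, 5.2.4 and 5.5 are partly blacked out, derivation details are in a separate document, and the CRF is not supplied. A rule or a reason field may exist there.

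**Conclusion.** The concern holds as a gap in the analysis of one secondary endpoint. The contraindications apply to performing the test, missing results are not imputed, the one visible test is at Week 26, and no sensitivity analysis addresses death or inability to walk. The comparison is therefore among subjects alive and able to walk at Week 26.

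Its size cannot be fixed from the documents. The 63–78% retention assumes normal changes with equal SD, a common cut-off, 10–20% of placebo untestable and a true difference of 0.3–0.5 SD. With about 20 placebo subjects, that is 2–4 people.

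This is an unadjusted secondary endpoint in a proof-of-concept study, and the primary FVC result is untouched. The case for acting is that the remedy is cheap. The protocol already uses the principle: Protocol 7.3.4.2 counts death together with a decline of 10 points or more in percent predicted FVC.

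**What to change.** Keep the ANCOVA as the estimate in metres. Leave the contraindications as they are. Prespecify one supplementary Week 26 rank comparison, either rank ANCOVA on baseline distance or a van Elteren test stratified by standard of care:

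- Rank death lowest, then test not done because of hypoxia or physical inability, then observed Week 26 distances.
- Do not carry an EOT walk done before Day 163 forward as a Week 26 value. In a progressive disease this would flatter the arm with more early stops.
- Leave administrative and COVID-19 misses as missing.
- Run the ranking with and without purely cardiac contraindications in the inability category, since these need not reflect IPF progression.
- Tabulate by arm the reason for each missing Week 26 walk, capturing the reason if the CRF does not already do so.
- Point the Section 6.2 reference in SAP 3.4.1.2 to a section that exists.

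The cost is one extra analysis and possibly one CRF field. The rank result has no metre scale, and its estimand mixes death and inability with distance, so it supplements the ANCOVA and does not replace it.

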5.2.3.3. Change from Baseline in SGRQ over 26 Weeks

The St. George's Respiratory Questionnaire (SGRQ) is a 50-item paper questionnaire split into 3 domains:

- symptoms (assessing the frequency and severity of respiratory symptoms),
- activity (assessing the effects of breathlessness on mobility and physical activity),
- impact (assessing the psychosocial impact of the disease).

Scores are weighted such that every domain score and the total score range from 0 to 100, with higher scores indicating a poorer health-related quality of life.

Note that before completing the questionnaire the subject will have to answer a question on his/her present health. This info will be tabulated.

Table 4 SGRQ Questions/Items and Their Weights (from 0 to 100)

General			
Q#	Question	Answer	Weight
	Check how you describe your current health	Very good	NA
		Good	NA
		Fair	NA
		Poor	NA
		Very poor	NA
Part 1			
Describe how often your respiratory problems have affected you over the past 3 months.			
Q#	Question	Answer	Weight
1	Over the past 3 months, I have coughed:	Almost every day	80.6
		Several days a week	63.2
		A few days a month	29.3
		Only with respiratory infections	28.1
		Not at all	0.0
2	Over the past 3 months, I have brought up phlegm (sputum):	Almost every day	76.8
		Several days a week	60.0
		A few days a month	34.0
		Only with respiratory infections	30.2
		Not at all	0.0
3	Over the past 3 months, I have had shortness of breath:	Almost every day	87.2
		Several days a week	71.4
		A few days a month	43.7
		Only with respiratory infections	35.7
		Not at all	0.0
4	Over the past 3 months, I have had wheezing attacks:	Almost every day	86.2
		Several days a week	71.0
		A few days a month	45.6
		Only with respiratory infections	36.4
		Not at all	0.0
5	How many times during the past 3 months have you suffered from severe or very unpleasant respiratory attacks?	More than 3 times	86.7
		3 times	73.5
		2 times	60.3
		1 time	44.2
		None of the time	0.0
6	How long did the worst respiratory attack last?	A week or more	89.7
		3 or more days	73.5
		1 or 2 days	58.8
		Less than a day	41.9
7	Over the past 3 months, in a typical week, how many good days (with few respiratory problems) have you had?	No good days	93.3
		1 or 2 good days	76.6

		3 or 4 good days	61.5
		Nearly every day was good	15.4
		Every day was good	0.0
8	If you have a wheeze, is it worse when you get up in the morning?	No	0.0
		Yes	62.0
Part 2 – Section 1			
Q#	Question	Answer	Weight
9	How would you describe your respiratory condition?	The most important problem I have	83.2
		Causes me quite a lot of problems	82.5
		Causes me a few problems	34.6
		Causes me no problems	0.0
10	If you ever held a job:	My respiratory problems made me stop working altogether	88.9
		My respiratory problems interfere with my job or made me change my job	77.6
		My respiratory problems do not affect my job	0.0
Part 2 – Section 2			
Questions about what activities usually make you feel short of breath these days.			
I#	Question	Answer	Weight
11	Sitting or lying still.	False	0.0
		True	90.6
12	Washing or dressing yourself.	False	0.0
		True	82.8
13	Walking around at home.	False	0.0
		True	80.2
14	Walking outside on level ground.	False	0.0
		True	81.4
15	Walking up a flight of stairs.	False	0.0
		True	76.1
16	Walking up hills.	False	0.0
		True	75.1
17	Playing sports or other physical activities.	False	0.0
		True	72.1
Part 2 – Section 3			
Questions about your cough and shortness of breath these days.			
I#	Question	Answer	Weight
18	Coughing hurts.	False	0.0
		True	81.1
19	Coughing makes me tired.	False	0.0
		True	79.1
20	I am short of breath when I talk.	False	0.0

		True	84.5
21	I am short of breath when I bend over.	False	0.0
		True	76.8
22	My coughing or breathing disturbs my sleep.	False	0.0
		True	87.9
23	I get exhausted easily.	False	0.0
		True	84.0
Part 2 – Section 4			
Questions about other effects that your respiratory problems may have on you these days.			
I#	Question	Answer	Weight
24	My cough or breathing is embarrassing in public.	False	0.0
		True	74.1
25	My respiratory problems are a nuisance to my family, friends, or neighbors.	False	0.0
		True	79.1
26	I get afraid or panic when I cannot catch my breath.	False	0.0
		True	87.7
27	I feel that I am not in control of my respiratory problems.	False	0.0
		True	90.1
28	I do not expect my respiratory problems to get any better.	False	0.0
		True	82.3
29	I have become frail or an invalid because of my respiratory problems.	False	0.0
		True	89.9
30	Exercise is not safe for me.	False	0.0
		True	75.7
31	Everything seems too much of an effort.	False	0.0
		True	84.5
Part 2 – Section 5			
Questions about your respiratory treatment.			
I#	Question	Answer	Weight
32	My treatment does not help me very much.	False	0.0
		True	88.2
33	I get embarrassed using my medication in public.	False	0.0
		True	53.9
34	I have unpleasant side effects from my medication.	False	0.0
		True	81.1
35	My treatment interferes with my life a lot.	False	0.0
		True	70.3
Part 2 – Section 6			
Questions about how your activities might be affected by your respiratory problems.			
I#	Question	Answer	Weight
36	I take a long time to get washed or dressed.	False	0.0
		True	74.2

37	I cannot take a bath or shower, or I take a long time to do it.	False	0.0
		True	81.0
38	I walk slower than other people my age, or I stop to rest.	False	0.0
		True	71.7
39	Jobs such as household chores take a long time, or I have to stop to rest.	False	0.0
		True	70.6
40	If I walk up one flight of stairs, I have to go slowly or stop.	False	0.0
		True	71.6
41	If I hurry or walk fast, I have to stop or slow down.	False	0.0
		True	72.3
42	My breathing makes it difficult to do things such as walk up hills, carry things up stairs, light gardening such as weeding, dance, bowl, or play golf.	False	0.0
		True	74.5
43	My breathing makes it difficult to do things such as carry heavy loads, dig in the garden, or shovel snow, jog or walk briskly (5 miles per hour), play tennis, or swim.	False	0.0
		True	71.4
44	My breathing makes it difficult to do things such as very heavy manual work, ride a bike, run, swim fast, or play competitive sports	False	0.0
		True	63.5
Part 2 – Section 7			
Questions about how your respiratory problems usually affect your daily life.			
I#	Question	Answer	Weight
45	I cannot play sports or do other physical activities.	False	0.0
		True	64.8
46	I cannot go out for entertainment or recreation.	False	0.0
		True	79.8
47	I cannot go out of the house to do the shopping.	False	0.0
		True	81.0
48	I cannot do household chores.	False	0.0
		True	79.1
49	I cannot move far from my bed or chair.	False	0.0
		True	94.0
50	Tick the statement which you think best describes how your respiratory problems affects you:	It does not stop me from doing anything I would like to do	0.0
		It stops me from doing one or 2 things I would like to do	42.0
		It stops me from doing most of the things I would like to do	84.2
		It stops me from doing everything I would like to do	96.7

Domain scores and total score:

- Symptoms score: questions 1-8.
- Activity score: questions 11 to 17 and 36 to 44.

- Impacts score: questions 9-10, 18 to 35, and 45 to 50.
Total score: all questions.

Each domain score is calculated separately in 3 steps

- The weights for all items are summed.
- The maximum weights for missed items are deducted from the maximum possible weight for each component. The maximum weights for all missed items are deducted from the maximum possible weight for the total score.

Sum of maximum possible weights for each score:

- Symptoms: 662.5
- Activity: 1209.1
- Impacts: 2117.8
- Total: 3989.4

- The score is calculated by dividing the summed weights by the adjusted maximum possible weight for that component and expressing the result as a percentage

$$\text{Score} = 100 \times \frac{\text{summed weights in that component}}{\text{sum of maximum weights for all non-missing items in that component}}$$

The total score is calculated in a similar way:

$$\text{Score} = 100 \times \frac{\text{summed weights in the questionnaire}}{\text{sum of maximum weights for all non-missing items in the questionnaire}}$$

Note that the questionnaire requests a single response to questions 1-7, 9-10, and 50. If multiple responses are given to one of these questions then the weights for the responses for that question will be averaged.

In case of missing items, the following rules will be applied:

- The symptoms score will only be calculated when no more than 2 items are missing.
- The activity score will only be calculated when no more than 4 items are missing.
- The impacts score will only be calculated when no more than 6 items are missing.
- The total score will only be calculated when the 3 domain scores could be calculated.

Source: St. George's Respiratory Questionnaire Manual (2009).

For actual values and changes from baseline in SGRQ total score, as well as symptom, activity, and impact scores, descriptive statistics will be provided per time point and treatment group. Results will also be graphically displayed by means of subject profile plots, boxplots over time

by treatment group for the actual values, and line plots of the mean (+/- SE) over time by treatment group for changes from baseline.

The change from baseline in SGRQ score (total, symptom, activity and impact) over 26 weeks will be compared between treatment groups by means of an ANCOVA model at each planned time point (as specified in Section 2.5 and 3.3.3) including treatment and stratum as categorical covariates and baseline SGRQ score as continuous covariates. LS means and 95% CIs will be presented per time point and treatment group as well as the LS mean differences between treatment groups with 95% CI.

The proportion of SGRQ responders at Week 26 (defined as absolute change from baseline in SGRQ total score ≤ -4 %, at least once) will also be tabulated per treatment group. Treatment effect on SGRQ responders will be assessed using the Fisher's exact test.

5.2.4. Other Endpoints

[REDACTED]

[REDACTED]

[REDACTED]

[REDACTED]

[REDACTED]

[REDACTED]

[REDACTED]

[REDACTED]

[REDACTED]

[REDACTED]

[REDACTED]

[REDACTED]

[REDACTED]

[REDACTED]

[REDACTED]

[REDACTED]

[REDACTED]

[REDACTED]

[REDACTED]

[REDACTED]

[REDACTED]

[REDACTED]

[REDACTED]

[REDACTED]

- [REDACTED]

[REDACTED]

- [REDACTED]

[REDACTED]

[REDACTED]

[REDACTED]

[REDACTED]

[REDACTED]

[REDACTED]

[Redacted]

- [Redacted]
- [Redacted]
- [Redacted]
- [Redacted]
- [Redacted]

[Redacted]

[Redacted]

[Redacted]

[Redacted]

[Redacted]

[Redacted]

[Redacted]

[Redacted]

[Redacted]

[REDACTED]

[REDACTED]

[REDACTED]

[REDACTED]

- [REDACTED]

- [REDACTED]

[REDACTED]

[REDACTED]

5.2.5. Subgroup Analyses

Descriptive statistics of the spirometry parameters will be provided by stratum (3 strata; pirfenidone, nintedanib, neither). In addition, for the primary endpoint a similar ANCOVA model with an additional term for treatment-by-stratum interaction will be used to estimate the LS means per treatment group and LS mean differences (with 95% CIs) for each stratum.

[REDACTED]

Summaries may also be provided for the efficacy [REDACTED] endpoints [REDACTED] [REDACTED] data will be available in time.

5.3. Safety Analyses

Safety analyses will be performed on the FAS.

Safety tables will be presented by treatment group.

Safety parameters will be analyzed descriptively (see Section 3.5.2 and Section 3.5.3). No formal testing will be performed to compare the treatment groups.

5.3.1. Adverse Events

All AEs and changes in attributes (worsening and improvement) of AEs are reported in the database. An identification number serves to link the records considered by the investigator as describing the evolution of one and the same event.

5.3.1.1. Definition of Treatment-Emergent Adverse Events

The analysis of AEs will be based on treatment-emergent events (TEAE). TEAEs are defined as

AEs (or worsening⁶ of an existing event) having a start date equal or after the date of the first administration of study drug and before the last dosing date plus 30 days. Improvements are not considered treatment-emergent.

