7.3.5.2. Adverse Events

Clinical and laboratory AEs will be coded using the latest version of the Medical Dictionary for Regulatory Activities. System organ class), High Level Group Term, High-Level Term, Preferred Term, and Lower-Level Term will be attached to the clinical database.

The following AEs will be considered as treatment-emergent adverse events (TEAEs):

Any AE (or worsening of any AE) with an onset date on or after the IMP start date and no later than 30 days after last dose of IMP.

Summaries (number and percentage of subjects) of TEAEs by System Organ Class and Preferred Term will be provided by treatment group. TEAEs will also be summarized by causal relationship to IMP or standard of care and by severity. In addition, TEAEs leading to premature discontinuation or dose reduction of IMP will be summarized. All AEs, non-treatment-emergent AEs, SAEs, AEs leading to hospitalization, AEs leading to death, deaths, AEs leading to discontinuation of IMP/standard of care and AEs leading to temporary stop or dose-reduction of IMP/standard of care will be listed.

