3.3.2. Analysis Periods

All event-type data (e.g. adverse events) and assessments will be allocated to analysis periods according to [Table 1](#).

Table 1 Analysis Periods

Analysis Period	Start Analysis Period	End Analysis Period
Screening	Date of signing the ICF	Date of first study drug administration - 1 day
Treatment	Date of first study drug administration	Date of last study drug administration + 30 days
Follow-up [#]	End date of the preceding analysis period + 1 day	Date of last contact

ICF: informed consent form

[#] If the last study drug administration plus 30 days is after date of last contact, the study will not include a follow-up period. The last analysis period will end on the date of last contact.

If times are collected or other information with respect to timing (e.g. before or IMP intake) this information will be taken into account in addition to the dates. The last analysis period will always end on the date of last contact.

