5.3.1.3. Allocation of Adverse Events to Analysis Periods

All AEs will be placed into analysis periods considering their start date, aiming to report the incidence of these events only in the analysis period during which they started.

The general rule for allocation of AEs to analysis periods follows:

$$\text{Analysis period start date} \leq \text{AE start date} \leq \text{analysis period end date}$$

If the start date of an AE is missing or incomplete to a level preventing a clear allocation of the AE to one single analysis period and no flag indicating timing relative to study medication is available, a worst-case consideration (see below) will be done aiming to allocate the AE to one single analysis period, if possible. When a worst-case consideration is needed, the end date of the AE, if and as available, should also be considered; if such AEs clearly end on a given point, this will exclude the possibility to allocate the AE to an analysis period after that point.

- An AE which according to the available information of its start date could belong to the screening as well as to the treatment period will only be placed in the treatment period.

⁶ 'Worsening' is defined as worsening in at least one of the following attributes: seriousness, severity, relationship and/or action taken.

- An AE which according to the available information of its start date could belong to the treatment period as well as to the follow-up period will only be placed in the treatment period.
- An AE with a missing start date will be allocated to the treatment period.

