5.3.1.7. Presentation of Results

The analysis will focus on AEs reported during the treatment period. AEs reported during the screening or follow-up period will only be listed.

All adverse events tables will show the number of subjects with TEAEs.

A summary table will be provided, showing the number (percent) of subjects with at least one:

- TEAE
- serious TEAE
- TEAE leading to death
- TEAEs by worst severity
- TEAE that was considered related to GLPG1205/placebo
- TEAE that was considered related to pirfenidone
- TEAE that was considered related to nintedanib
- TEAE for which GLPG1205/placebo was reduced
- TEAE for which GLPG1205/placebo was temporarily stopped
- TEAE for which GLPG1205/placebo was permanently stopped
- TEAE for which pirfenidone was reduced
- TEAE for which pirfenidone was temporarily stopped
- TEAE for which pirfenidone was permanently stopped
- TEAE for which nintedanib was reduced
- TEAE for which nintedanib was temporarily stopped
- TEAE for which nintedanib was permanently stopped

For each line, the difference in percentage of subject with an AE between placebo and GLPG1205 will be included, together with the 95% CI of the difference using the method of Miettinen and Nurminen.

Frequency tabulations, by system organ class and preferred term, of the number (percent) of subjects with a TEAE will be presented. Similar tables will be provided (by worst severity) for TEAEs of grade 3/4, TEAEs related to GLPG1205/placebo and for TEAEs related to SOC.

Serious adverse events (including AEs leading to hospitalization), AEs leading to death, leading to respiratory-related hospitalization (as reported by the investigator), of grade 3/4, leading to discontinuation of GLPG1205/placebo, leading to a temporary stop or dose reduction of GLPG1205/placebo, leading to a permanent stop, temporary stop, or dose reduction of SOC, pre- and post-treatment adverse events will be listed.

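### SAP 5.3.1.1 ends the TEAE window one day earlier than the protocol and SAP Table 1, so an AE starting 30 days after last dose is left out of every TEAE table

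*SAP*

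**What the plan says.** Day +30 below means the calendar date of the last dose plus 30 days.

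- **Protocol 7.3.5.2** defines a TEAE as a new or worsened AE with onset from the IMP start date and "no later than 30 days after last dose of IMP".
- **SAP 5.3.1.1** keeps the same start but requires the event to begin "before the last dosing date plus 30 days".
- **SAP 3.3.2, Table 1** ends the treatment period on "Date of last study drug administration + 30 days" and starts follow-up on "End date of the preceding analysis period + 1 day".
- **SAP 5.3.1.3** places an AE in a period when its start date is on or after the period's start and on or before the period's end.
- **SAP 5.3.1.7** says "All adverse events tables will show the number of subjects with TEAEs". It adds that "AEs reported during the screening or follow-up period will only be listed", and that "pre- and post-treatment adverse events will be listed".
- **SAP 5.3.1.9** builds the EudraCT serious and non-serious tables from TEAEs as well.

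SAP 5.5, which records departures from the protocol, declares no change to the TEAE definition in its legible text.

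**The concern.** Three rules include Day +30 (the protocol definition, Table 1 and the allocation rule) and one excludes it (SAP 5.3.1.1). The one that excludes it decides what the AE tables count.

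An event starting on Day +30 therefore has a mixed status in the SAP: inside the treatment period but not treatment-emergent. It would be missing from the overall summary table, with its Miettinen–Nurminen intervals for the treatment difference, from the tables by system organ class and preferred term, and from the EudraCT tables. Protocol 9.3.2 requires SAEs within 30 days of last dose to be reported whatever their cause, so a Day +30 SAE could be collected and reported and still be missing from the serious TEAE count.

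The exclusion also conflicts with the SAP's handling of related data. Laboratory, ECG and vital-sign abnormality analyses focus on the treatment period, which includes Day +30. An abnormality found that day could be tabulated while the AE recorded for it is not. SAP 5.3.1.3 also assigns an AE with a missing start date to the treatment period. An event known to start on Day +30 then fails the TEAE test, although the general approach in doubtful cases is to include.

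**Working it through.** The plan states no figure to reproduce, so the check is date logic. Let L be the date of last dose and S the AE start date, with S on or after first dose.

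- Protocol 7.3.5.2: TEAE if S ≤ L + 30.
- SAP 5.3.1.1: TEAE if S < L + 30.
- SAP Table 1 with 5.3.1.3: treatment period if S ≤ L + 30; follow-up if S ≥ L + 31.

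| S | Protocol TEAE | SAP 5.3.1.1 TEAE | SAP period |
|---|---|---|---|
| L + 28 | yes | yes | treatment |
| L + 29 | yes | yes | treatment |
| **L + 30** | **yes** | **no** | **treatment** |
| L + 31 | no | no | follow-up |
| L + 32 | no | no | follow-up |

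(Last contact is taken to be late enough for a follow-up period to exist.) Day +30 is the only day on which the rules disagree.

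**Size of the gap.** Assume uninterrupted dosing for the planned 26 weeks: 26 × 7 = 182 days.

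- Protocol window: 182 + 30 = 212 days.
- SAP 5.3.1.1 window: 182 + 29 = 211 days.
- Difference: 1 day, and 1/212 = 0.47%.

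At the limits of the COVID-19 window for Visit 9 (−28 to +56 days around Week 26), dosing would last 154 to 238 days. The share is then 1/184 = 0.54% to 1/268 = 0.37%.

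**Can an event with that start date be collected?** Visit 10 is planned 4 weeks after last dose (protocol 4.2) with a window of ±4 days (protocol 6.1), so it falls on Day +24 to Day +32. AE reporting ends at that visit (protocol 6.5.1 and 9.3.1).

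- Visit 10 on Day +24 to +29 (6 of the 9 allowed days): a new non-serious AE starting on Day +30 falls after the reporting period.
- Visit 10 on Day +30 to +32 (3 of the 9 days): it can be recorded.
- Under the COVID-19 addendum to protocol 6.1.1 (−7 to +28 days), Visit 10 can fall on Day +21 to +56. Of these 36 days, the 27 from Day +30 onward allow it to be recorded.
- SAEs are reportable through Day +30 whenever Visit 10 takes place (protocol 9.3.2).

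These are counts of allowed days. The documents do not say how visits will be spread over them.

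**The case against.** The strongest reply is that this is loose drafting with little consequence. SAP 5.3.1.7 says the analysis focuses on AEs in the treatment period, which includes Day +30, and derivation details are deferred to a separate document (SAP section 1) that may settle the boundary. Safety is descriptive without formal testing (SAP 5.3), and the rule is identical in both arms. All of this bears on importance, and it is a fair argument for a low rank. It does not remove the conflict: 5.3.1.1 is the operative definition, and a programmer following it literally would exclude Day +30.

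A reader might go further and infer that a Day +30 event disappears altogether, being neither a TEAE for the tables nor a follow-up event for the post-treatment listing. The documents do not support that:

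- Protocol 7.3.5.2 plans listings of all AEs and of non-treatment-emergent AEs; a Day +30 event that fails the SAP test belongs in both.
- SAP 4.2 includes an all-AE summary listing among interim outputs that it describes as a subset of the final analyses.
- SAP 5.3.1.7 lists SAEs, deaths, grade 3/4 AEs and AEs leading to action on study drug or standard of care by attribute, with no TEAE condition stated.
- The SAP does not define post-treatment separately. Equating it with the follow-up period is a natural reading, but not the only one.

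Nor do the documents give an AE rate from which to estimate how many events are affected.

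**Conclusion.** The inconsistency is real and confined to one day. On the literal wording, an AE starting on Day +30 is a TEAE under the protocol and falls in the SAP's treatment period, but is left out of every SAP TEAE table. What is at stake is the correctness of the counts; the event should remain visible in listings.

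The size is 1 day in 212, about 0.5% of the window, assuming 182 days of dosing. No event count is offered, and no efficacy result is affected. The conclusion rests on reading 'before' as strict, and on no change having been declared in the redacted part of SAP 5.5 or in the separate derivations document. This is a minor point, worth correcting because the SAP should match the protocol's safety definition and its own Table 1.

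**What to change.** In SAP 5.3.1.1, change 'before' to 'on or before' ahead of the limit of last dosing date plus 30 days. That matches protocol 7.3.5.2, Table 1 and the allocation rule in 5.3.1.3. Every AE start date from first dose onward is then either in the treatment period and eligible as a TEAE (through Day +30) or in follow-up and listed only (from Day +31).

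The cost is two words in the SAP and a check that the derivations document uses the same boundary. No new data are needed and no other analysis changes. It is best made before unblinding, so that the choice cannot be linked to the data.
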